11.5.5 Secondary Analysis

An analysis similar to that described in the primary analysis will be performed for scores obtained at 5 weeks. Additionally, a repeated measures model including a random effect for subject will be estimated for the binary neuropathy improvement score measured at baseline,

week 5 and week 10. Additional baseline factors as previously described above may be added to this model as well.

The secondary endpoint composite measure of specific CIPN symptoms will be treated as a continuous measure and analyzed using analysis of variance techniques. The secondary endpoints measured on a 5-level ordinal scale will be summarized with frequencies and proportions and analysis of variance techniques on the ranks test will be used to test for differences by arm. The number of unhealthy days and activity limitation days will be analyzed using analysis of variance techniques.

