5.4 Questionnaires

Questionnaires will be administered privately, preferably **prior** to the acupuncture session for those on intervention arm. All subjects will be able to answer the questionnaires via two options: 1) on paper (in person or via certified mail) or 2) via RedCap electronic survey. Phone contact for questionnaires is acceptable if unable to be completed by other stated routes. The form of questionnaire administration will be based on the appointment situation, needs and/ or preference of the subject, and subject access to technology (e.g., computer, tablet, smartphone).

Questionnaires to be completed at Baseline, midpoint and endpoint visits, even if those on the acupuncture arm have not received the acupuncture session on schedule or if sessions are missed.

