11.2 Sample Size

This study is designed with a primary objective to evaluate the effectiveness of acupuncture versus standard subject management in terms of reduction of neuropathy in actively treated multiple myeloma subjects diagnosed with CIPN. A Fisher's Exact Test with a two-sided alpha = 0.20 significance level will have at least 80% power to detect the difference between a standard of care group proportion of 0.10 and a treatment group proportion of 0.35 when the sample sizes are at least 22 and 44 evaluable subjects, respectively. In order to identify at least 66 evaluable subjects, we anticipate enrolling 75 subjects.

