11.3 Endpoints

11.3.1 Definition of Primary Endpoint

The primary endpoint for this study is a binary variable that will be determined for each subject indicating whether or not they experienced at least a 2-point improvement in neuropathy between the baseline score and the score obtained at Week 10 (+/- 1 week).

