11.5.4 Primary Analysis

The frequency and proportion of subjects who experienced at least a 2-point improvement in neuropathy between the baseline score and the score obtained at Week 10 (+/- 1 week) will be calculated for each study arm. A two-sided Fisher Exact test will be executed, testing the null hypothesis that there is no difference in neuropathy improvement rate between the arms.

Additionally, logistic regression will be used to evaluate the impact of acupuncture while adjusting for potential baseline confounding factors, including the stratification variable, baseline neuropathy severity grade. Univariate models will be used to identify baseline factors that are individually prognostic. Statistically significant factors identified from the univariate models will then be included in a multivariable model. Backward elimination will be used to identify baseline factors that are independently prognostic. A treatment indicator variable will be added to obtain an adjusted odds ratio.

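### The repeated-measures model in 11.5.5 lists baseline as an outcome time for an improvement-from-baseline indicator that is 0 there for every subject

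*Combined protocol and SAP*

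**What the plan says.** Section 11.3.1 defines the primary endpoint as a binary variable "indicating whether or not they experienced at least a 2-point improvement in neuropathy between the baseline score and the score obtained at Week 10". Section 11.5.4 uses the same contrast, "between the baseline score and the score obtained at Week 10 (+/- 1 week) will be calculated for each study arm". Section 11.5.5 repeats that analysis for the Week 5 score and then adds a further model: "a repeated measures model including a random effect for subject will be estimated for the binary neuropathy improvement score measured at baseline", with Weeks 5 and 10 completing the list of times. It does not say how time enters the model or which fixed effects it contains, beyond this: "Additional baseline factors as previously described above may be added to this model as well". The earlier description of those factors is in 11.5.4, which mentions "including the stratification variable, baseline neuropathy severity grade".

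The 0-10 score is first taken once, after consent and before the other baseline procedures (Section 6, footnote 11; Section 7.1.1). The study therefore holds no earlier score against which a baseline improvement could be calculated.

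**The concern.** A change-from-baseline indicator cannot vary at baseline. If an analyst follows 11.5.5 to the letter, one third of the rows are zeros by definition. These rows carry no treatment information, but they enter the likelihood, and what they do there depends on a time coding that the plan leaves open. At stake is the output of a prespecified secondary model of the primary outcome: either a term that cannot be estimated, or a printed odds ratio, subject variance and visit rates that reflect an unrecorded programming choice.

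**Working it through.** **1. The plan's own figure.** Section 11.2 claims at least 80% power for Fisher's exact test at two-sided alpha 0.20, with "a standard of care group proportion of 0.10 and a treatment group proportion of 0.35" and 22 and 44 subjects. Exact enumeration of all 23 × 45 tables gives 81.7%. The figure is reproduced, and the repeated-measures model has no bearing on it.

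**2. The indicator at baseline.** Write I(t) = 1 if Y(0) − Y(t) ≥ 2, and 0 otherwise. At t = 0, Y(0) − Y(0) = 0 < 2, so I(0) = 0 for all. Rows: 66 × 3 = 198 at most (Week 5 may be missing), of which 66, or 66/198 = one third, are constant. Without baseline there are at most 66 × 2 = 132.

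**3. Model and inputs.** logit P(I = 1 | u) = intercept + time + β × arm + u, with u normal with standard deviation σ. From 11.2: 22 control and 44 acupuncture subjects, Week 10 rates 10% and 35%. Assumed, because the documents do not give them: Week 5 rates 7% and 25%, σ = 2 (the middle case). The expected log-likelihood was maximised over exact response-pattern probabilities with 60-point quadrature. The wider range crossed Week 5 rates of 5/15%, 7/25% and 10/35% with σ of 1, 2 and 3 (nine cases).

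**4. Categorical visit.** Each baseline row contributes a factor 1 − p(0), which rises towards 1 as the baseline coefficient falls without limit. No finite maximum exists, and the likelihood approaches that of the model without baseline rows. With the coefficient held at −12, −20 and −30, β is 2.27, 2.30 and 2.30, against 2.30 without baseline rows.

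**5. Linear time or no time term.** The model converges (rates are control/acupuncture):

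| Middle case | Fitted σ | Week 10 population-averaged log-OR | Arm likelihood-ratio statistic | Fitted Week 5 | Fitted Week 10 |
|---|---|---|---|---|---|
| No baseline rows, categorical visit | 2.0 | 1.51 | 6.61 | – | – |
| Baseline rows, linear time | 1.69 | 1.49 | 6.76 | 3.5%/16.2% | 12.5%/38.7% |
| Baseline rows, no time term | 0.89 | 1.43 | 6.78 | 5.6%/20.0% | 5.6%/20.0% |
| True values | 2.0 | – | – | 7%/25% | 10%/35% |

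The linear model also fits improvement rates of 0.8%/4.9% at baseline, where they are 0%.

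**6. Like for like, no time term.** Dropping time misfits the rates by itself, so the fair comparison omits time from both models:
- Without baseline rows: β = 2.21, σ = 1.87, fitted rates 8.5%/30.0%.
- With baseline rows: β = 1.55, σ = 0.89, fitted rates 5.6%/20.0%.

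Simple averages agree closely. Control: (7 + 10)/2 = 8.5% and (0 + 7 + 10)/3 = 5.7%. Acupuncture: (25 + 35)/2 = 30.0% and (0 + 25 + 35)/3 = 20.0%.

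**7. The treatment comparison.** Over the nine cases, baseline rows move the population-averaged arm effect by +0.5% to −8.2% and the arm statistic by +0.2% to +3.9%. Like for like without a time term, the ranges are −5.6% to −8.2% and +0.3% to +3.9%.

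**The case against.** The best defence is that the sentence is loose wording. Section 5.4 has "Questionnaires to be completed at Baseline, midpoint and endpoint visits", so the authors may have meant the score from which improvement is derived. That is plausible and cannot be excluded. But the object of the sentence is the binary improvement score, baseline is listed as a time at which it is measured, and nothing else in the plan stops an analyst from building the row.

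Three further objections stand and limit the point. Under categorical visit, the common arm estimate does not change. The distortions need a coding that the plan does not specify, and their sizes rest on assumed Week 5 rates and σ. No decision rule is attached to this model.

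A reader might also infer more than the documents support:
- *That the treatment effect is biased downwards by about 30%* (1.55/2.21 = 0.70). The two coefficients are conditional on subject effects with different fitted σ, so they are not on a common scale. The population-averaged effect and the arm statistic, which can be compared, move little.
- *That the baseline rows explain the whole gap between 5.6%/20.0% and the true Week 10 rates of 10%/35%.* Omitting time accounts for 10 − 8.5 = 1.5 of the 4.4 control points and 35 − 30 = 5.0 of the 15.0 acupuncture points, about one third.
- *That the primary result or the power is at risk.* The Fisher test in 11.5.4 and the separate Week 5 comparison do not use this model.

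**Conclusion.** The wording is wrong as it stands, and the point is minor. That the indicator is 0 at baseline, that this affects one third of the rows, and that the baseline term has no finite estimate under categorical visit all follow from the plan's own definitions. Under linear time or no time term, the printed conditional odds ratio, subject SD and fitted rates are distorted; the sizes shown hold for the assumed middle case. The treatment comparison in this model is little affected, and the primary test, its power and the separate Week 5 analysis are not affected.

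**What to change.** In 11.5.5, change the list of outcome times to *at Week 5 and Week 10 (improvement from baseline)* and state that visit enters as a categorical term. Baseline neuropathy remains available as a covariate, as 11.5.5 already allows. If the authors want baseline kept as an outcome time, the alternative is to model the 0-10 score itself at the three visits instead of the binary indicator.

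The cost is a few words. No new data are needed, the primary endpoint, sample size and analysis population stay as they are, and no treatment information is lost by dropping the baseline rows.

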1.2 Study Rationale and Study Design

This randomized, controlled trial (see Schema) is designed to evaluate the effect of acupuncture on CIPN, other symptoms, and potential opioid and concomitant medication sparing effects in comparison to standard of care management in MM subjects. We hypothesize that acupuncture will be associated with: 1) a clinically significant and statistically significant reduction in CIPN; 2) statistically significant reduction of other symptoms such as nervousness and lack of energy; and 3) statistically significantly improved QOL at ten weeks. We also theorize that acupuncture will be opioid and concomitant medication sparing at ten weeks. We expect that the dose of acupuncture received will impact the outcomes, with higher doses of acupuncture being associated with better outcomes.

This study is novel in that it will be, to our knowledge, 1) the largest randomized, controlled trial to examine the effect of acupuncture on CIPN in MM patients 2) the first to explore the impact of acupuncture on opioid and concomitant medication intake.

This project aims to strengthen the care of persons with MM by improving quality of life (QOL) and ability to perform daily activities through reduced CIPN symptoms. CIPN debilitates and erodes QOL by preventing individuals from pursuing their normal activities of daily living. The features of CIPN, including physical, social/family, emotional, functional, and specific CIPN

symptoms, will be measured with the validated FACT-GOG-NTX.⁵⁸ This project brings necessary attention and scientific inquiry to supportive cancer care, which is sometimes de-prioritized behind disease treatment.^{59,60} The potential for nonpharmacologic acupuncture to reduce CIPN and other symptoms with minimal side effects has beneficial implications for disease treatment. Patients with controlled symptoms are better able to tolerate life-prolonging treatment and avoid chemotherapy dose reductions which result from neurotoxic side effects of chemotherapy.^{11,61,62}

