5.3.3 Opioid Intake

The electronic medical record will be consulted for opioids in the opioid medication list and verified with the subject. Subjects will be asked if there are any other opioids they are taking which might not be documented in the EMR. This information will be collected at the baseline, midpoint and endpoint visit. Subjects will be asked to provide the information based on a past 7-day recall. The self-reported quantities will be converted to Morphine Equivalent Daily Dose (MEDD), using an opioid conversion calculator (See Appendix B).

These opioids include but are not limited to:

- fentanyl (such as Fentora®)
- hydromorphone (such as Dilaudid®)
- long-acting hydromorphone (Exalgo®)
- oxycodone (such as Oxycontin®)
- oxycodone with acetaminophen (such as Percocet®)
- oxymorphone (such as Opana®)
- hydrocodone with acetaminophen (such as Vicodin®, Hycet®)
- tramadol (such as Ultram®, Conzip®)
- morphine (such as MS-Contin®)
- methadone (such as Methadose, Dolophine®)

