⁵ For acupuncture arm, Midpoint occurs at Week 5 ± 1 week from first acupuncture session, with Endpoint occurring at Week 10 ± 1 week from first acupuncture session. For control arm, Midpoint occurs at Week 5 ± 1 week from Randomization with Endpoint occurring at Week 10 ± 1 week from Randomization.

⁶ Collect MM date of diagnosis and staging at Baseline

⁷ If a subject decides or needs to be withdrawn from the study early (all visits and acupuncture assessments, if applicable), but is willing to complete an Early Termination visit, subject will complete assessments a final time, and will be considered Off Study (See section 8.2). Subjects do not need to complete questionnaires if they have done so within the last 2 weeks.

⁸ AESIs should only be collected on subjects randomized to acupuncture arm, beginning with first acupuncture session until 30 days after final acupuncture session.

⁹ For collection of opioid medication intake and concomitant medications, collect what has been taken over the past 7 days.

¹⁰ Collect chemotherapy regimen information throughout the study (if applicable).

¹¹ CIPN Neuropathy 0-10 & neuropathy physical location questionnaire is to be completed the first time **after consenting and prior to any other baseline procedures or assessments** to determine if the subject qualifies for enrollment into the study (see section 7.1.1).

¹² Notify subject of their randomization result.

¹³ Follow Up on AESIs: Can be done over the phone- this follow up for AESIs is only for subjects randomized to Acupuncture treatment arm.

¹⁴ Questionnaire may be completed after consent and prior to or after Randomization

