7. ADDITIONAL INFORMATION ON STUDY PROCEDURES

7.1.1 Screening/Baseline

Subjects will be consented to the trial, and the CIPN Neuropathy 0-10 (and physical location) questionnaire will be administered. Subjects who score <2 on the CIPN Neuropathy 0-10 questionnaire will be a screen failure and will not be randomized or enrolled into the study. If CIPN Neuropathy 0-10 is answered sufficiently for inclusion (score ≥ 2), the rest of the baseline assessments are to be completed within two weeks from consent. Once eligibility is confirmed, subject will be randomized via CTMS to either Acupuncture (intervention arm) or Standard of Care. Subjects will be notified of their randomization result. Those randomized to Intervention Arm will begin acupuncture sessions within two weeks of enrollment.

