11.5.7 Exploratory Analysis

The exploratory endpoint of Morphine Equivalent Daily Dose (MEDD) will be treated as a continuous measure and analyzed using analysis of variance techniques. Total counts and descriptive statistics of class and dose of concomitant medication use will be summarized by study arm.

In order to evaluate the dose response, dose will be treated as a categorical variable with levels of no acupuncture (0 sessions), low dose (1 – 3 sessions), medium dose (4 – 7 sessions), high dose (8 – 11 sessions) and complete dose (12 sessions). Logistic regression will be performed to investigate the association between dose of acupuncture and CIPN improvement. Acupuncture expectancy will be determined for each subject as a composite measure, which is calculated as the sum of the responses to the four questions on the acupuncture expectancy scale. Logistic regression will be used to evaluate the effect of acupuncture expectancy on the primary endpoint, 2-point improvement in neuropathy.

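### Secondary scores and MEDD have no stated model: specify Week 10 ANCOVA with baseline and stratum, take baselines before the arm is known, and fix the supplementary logistic model

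*Combined protocol and SAP*

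**What the plan says.** **Secondary and exploratory models.** Section 11.5.5 states: "The secondary endpoint composite measure of specific CIPN symptoms will be treated as a continuous measure and analyzed using analysis of variance techniques". For the CDC quality-of-life counts it states: "The number of unhealthy days and activity limitation days will be analyzed using analysis of variance techniques". Section 11.5.7 states: "The exploratory endpoint of Morphine Equivalent Daily Dose (MEDD) will be treated as a continuous measure and analyzed using analysis of variance techniques". The five-level items get analysis of variance on ranks, compared by arm. Sections 11.3.2 and 11.3.4 define the scales but not whether the outcome is the Week 10 value or the change. The only covariate sentence in 11.5.5 is optional and belongs to the repeated binary neuropathy model. Section 1.2 hypothesises "statistically significantly improved QOL at ten weeks" and also looks to ten weeks for opioid sparing, but section 11.5 does not carry that time point over. Baselines are collected. Of opioid intake, section 5.3.3 says: "This information will be collected at the baseline, midpoint and endpoint visit".

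**Baseline timing.** Section 7.1.1 says that, once the neuropathy score qualifies the subject, "the rest of the baseline assessments are to be completed within two weeks from consent", and only then describes randomization. Footnote 14 of the study calendar says of the questionnaires: "Questionnaire may be completed after consent and prior to or after Randomization". The heading of the baseline column, which also holds opioid intake, allows collection after randomization too. Footnote 12 has subjects told their arm. Only the 0–10 neuropathy score is fixed first (footnote 11).

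**Supplementary logistic model.** Section 11.5.4 names the stratification variable among the adjustment factors. It then screens factors one at a time, applies backward elimination, and adds treatment last. It gives no candidate list or selection threshold and does not say that the stratum is retained.

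**The concern.** At least three analyses fit the secondary wording: a comparison of Week 10 values, a comparison of changes, and ANCOVA. They differ in power, and in an open-label trial the choice should not wait until the data are seen. Baselines already collected would sharpen these comparisons at no cost in subjects.

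That gain is safe only if the baseline is reported before the subject knows the arm. A self-report given after an open-label assignment may be coloured by it, and any analysis that uses it inherits the distortion.

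The adjusted odds ratio depends on a list and a threshold that nobody could reproduce from the text.

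**Working it through.** **1. The plan's own figure.** Section 11.2 gives 22 control and 44 acupuncture subjects, response rates 0.10 and 0.35, and a two-sided Fisher test at 0.20. Enumerating both binomials gives power 81.7%, which meets the stated 80%. Nothing below changes it.

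**2. Detectable difference for a continuous score.** The documents give no SD and no baseline-to-Week-10 correlation ρ, so results are in SD units and ρ = 0.3, 0.5, 0.7 is assumed. They give no level for the secondary tests, so 0.05 is assumed and shown beside 0.20, the only test level stated.

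- The standard error is s × √(1/22 + 1/44) = 0.261s.
- s = 1 for the Week 10 value, √(2(1−ρ)) for change, and √(1−ρ²) for ANCOVA.
- Degrees of freedom are 64, 64 and 62. ANCOVA spends two on baseline and stratum; the stratum is assumed to explain nothing further.
- The noncentral t is solved for 80% power.

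| Analysis | 0.05: ρ = 0.3 / 0.5 / 0.7 | 0.20: ρ = 0.3 / 0.5 / 0.7 |
|---|---|---|
| Week 10 ANOVA | 0.74 / 0.74 / 0.74 | 0.56 / 0.56 / 0.56 |
| Change ANOVA | 0.88 / 0.74 / 0.58 | 0.66 / 0.56 / 0.43 |
| ANCOVA | 0.71 / 0.64 / 0.53 | 0.53 / 0.48 / 0.40 |

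ANCOVA is best in every column. Relative to the Week 10 comparison, its residual variance is 1−ρ² = 0.91, 0.75, 0.51.

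**3. Skewed and ordinal outcomes.** These were simulated on assumed shapes: day counts with 30% at 0 and 10% at 30, MEDD with 60% at zero and a lognormal remainder, and five-level items cut at 35/25/20/12/8%. The latent effect was 0.6 SD, at level 0.05. Power at ρ = 0.3 / 0.5 / 0.7:

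| Outcome | Week 10 ANOVA | Raw ANCOVA | Rank ANCOVA |
|---|---|---|---|
| Day counts | 51–52% | 53 / 59 / 68% | 58 / 64 / 75% |
| MEDD | 41–42% | 41 / 44 / 53% | 46 / 49 / 57% |
| Five-level items | 53–54% (on ranks) | – | 56 / 60 / 71% |

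For MEDD, rank ANOVA with no baseline term already gives about 45–46% at ρ = 0.3. There, most of the gain comes from ranking and not from the baseline.

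**4. A baseline reported after the arm is known.** Assume a 0.2 SD shift in one arm's reported baseline and no true effect.

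- ANCOVA bias is 0.2ρ = 0.06, 0.10, 0.14 SD. Noncentrality 0.2ρ / (0.261√(1−ρ²)) = 0.24, 0.44, 0.75. False-positive rate at nominal 5%: 5.6, 7.2, 11.5%.
- Change bias is 0.20 SD. Noncentrality 0.2 / (0.261√(2(1−ρ))) = 0.65, 0.77, 0.99. False-positive rate: 9.8, 11.7, 16.4%.
- The Week 10 comparison does not use the baseline and is not biased.

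**5. Supplementary logistic model.** Expected responders: 22 × 0.10 + 44 × 0.35 = 2.2 + 15.4 = 17.6. With 10 independent null candidates (assumed), the chance of at least one false selection in the univariate screen is 1 − 0.95¹⁰ = 40% at threshold 0.05 and 1 − 0.80¹⁰ = 89% at 0.20. If the stratum is not forced in, simulation with 4 to 16 assumed noise candidates gives an adjusted odds ratio more than 20% away from the fixed model in 8–26% of trials (threshold 0.05) or 16–51% (0.20). The loss of power is small: 0.1–2.6 or 1.2–4.1 points.

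**The case against.** The strongest reply is that nothing here is wrong. Analysis of variance is a family that includes ANCOVA, section 1.2 points to ten weeks, and these are secondary or exploratory endpoints. That stands as far as it goes. A reader might infer that the plan rules out baseline adjustment or that its tests are invalid; the text supports neither. What remains is that the model is not stated.

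The gain can also be small. At ρ = 0.3 it is 0.03 SD at either level, and for MEDD ranking matters more than the baseline. Both stand, which is why the scale should be fixed as well as the covariates.

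On timing, the 0.2 SD shift is assumed. Section 7.1.1 suggests the safer order, section 5.4 prefers questionnaires before the acupuncture session, and a plain Week 10 comparison would be unharmed. A reader might infer that the baselines will be distorted, or that the primary endpoint is exposed. The documents show only that late completion is allowed, and the primary baseline is taken before randomization. MEDD draws on the medical record as well as recall and may be less exposed. The timing still matters for change scores and for the ANCOVA recommended here.

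On the logistic model, section 11.5.4 can be read as always keeping the stratum, and the power loss is slight. It calls the stratum a severity grade, and a reader might take this for the CTCAE grade in section 5.3.2. Section 4.1 has a single stratification factor, so the meaning is clear and the label is a minor wording point. The selection procedure also serves a stated aim of finding prognostic factors, so it should not simply be deleted.

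**Conclusion.** The point holds as an under-specification with a better method at hand. The secondary and MEDD analyses lack a baseline term, a stratum and an outcome form, and baseline ANCOVA improves on both plain readings for a continuous score. The gain runs from slight at ρ = 0.3 to substantial at ρ = 0.7 and rests on assumed correlations; the rank results also rest on assumed distributions. The timing passages disagree and should be reconciled, because a late baseline can inflate false positives in change or ANCOVA analyses by an amount that depends on an unknown shift. The adjusted odds ratio is not reproducible as written. The primary Fisher test and the sample size are untouched.

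**What to change.** 1. **Model (free).** In 11.5.5 and 11.5.7, analyse the Week 10 value by ANCOVA with that score's own baseline and the randomization stratum (2–6 vs 7–10). Use the raw scale for the neurotoxicity composite and ranks for the ordinal items, day counts and MEDD. The cost is wording and two degrees of freedom. The evaluable population in 11.4 requires only neuropathy scores, so also state how a missing secondary baseline is handled.
2. **Timing (cheap).** Reconcile footnote 14 and the baseline column with section 7.1.1, so that baseline questionnaires and MEDD recall are completed before the subject is told the arm. Footnote 14 already permits this order for the questionnaires. The cost is a longer pre-randomization visit and some questionnaire time spent on subjects who are then not randomized.
3. **Logistic model (cheap).** In 11.5.4, take the adjusted odds ratio from one fixed model: arm plus the stratum (2–6 vs 7–10), forced in. Keep the univariate and backward-elimination work as a separate descriptive look at prognostic factors, and name the stratum as in section 4.1. The cost is wording, and the adjusted odds ratio no longer draws on other prognostic factors. The Week 5 analysis, which follows the primary one, inherits the change. Fisher stays the primary test.

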1.1.3 Current Treatments for CIPN

There are no cures for CIPN; it can only be treated.¹⁷ Treatments for CIPN include concomitant medications which target various pathophysiological mechanisms. Pharmacologic options include anticonvulsants (e.g., gabapentin, (Neurontin®, Gralise®), antidepressants (e.g., duloxetine (Cymbalta®)), over-the-counter (e.g. aspirin, ibuprofen), prescription (e.g., celecoxib (Celebrex®)), non-steroidal anti-inflammatory drugs (NSAIDs), and opioids in severe cases unresponsive to other treatments. Topical agents (e.g., amitriptyline, lidocaine) applied to the skin are also options.^{18,19} These treatments, however, are not universally effective. Menthol and capsaicin can be used but¹⁸ have side effects and there is limited evidence to support their clinical use.⁶ Side effects of anticonvulsants include drowsiness and dizziness, and antidepressants are associated with dry mouth, nausea, drowsiness, dizziness, decreased appetite and constipation.²⁰ Nonpharmacologic options with varying levels of efficacy include neurostimulation, exercise, nonpharmacologic menthol and capsaicin topical agents, and

acupuncture.¹⁸ For patients open to integrative modalities to lessen CIPN symptoms, acupuncture is a promising intervention.

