 - The number of unhealthy days will be calculated as the average of the number of physically unhealthy days (CDC-HRQOL Question 2) and the number of mentally unhealthy days (CDC-HRQOL Question 3), with a maximum of 30 days.⁷⁴ This will be calculated for each subject as a quantitative value between 0 and 30, representing the number of days out of the past 30 that the subject's health was not good.
 - The number of activity limitation days assessed through CDC-HRQOL Question 4 will be calculated for each subject as a quantitative value between 0 and 30, representing the number of days out of the past 30 that the subject's health kept them from doing their usual activities.

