11.3.4 Definition of Exploratory Endpoints

- Opioid use
 - Opioid use assessed through Morphine Equivalent Daily Dose (MEDD) will be calculated for each subject as a quantitative value.
- Concomitant medication use
 - Concomitant medication use assessed through medication name and dose will be determined for each subject.
- Acupuncture administration
 - Acupuncture administration will be defined for each subject on the acupuncture arm as the number of attended acupuncture sessions from 0 to 12.
- Acupuncture expectancy
 - The acupuncture expectancy score will be captured quantitatively for each subject as a composite score ranging from 4 to 20.

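### Unhealthy days, activity-limitation days and opioid dose are compared by ANOVA with no stated adjustment for the subject's own baseline value, although the trial collects it

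*Combined protocol and SAP*

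**What the plan says.** The two day counts are secondary endpoints from the CDC HRQOL-4. On construction, Section 11.3.2 says: "The number of unhealthy days will be calculated as the average of the number of physically unhealthy days" and of the mentally unhealthy days. Activity-limitation days come from a single item. Both run from 0 to 30.

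MEDD is exploratory. Section 11.3.4: "Opioid use assessed through Morphine Equivalent Daily Dose (MEDD) will be calculated for each subject as a quantitative value". No upper limit is given.

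The analysis of the day counts is one sentence in Section 11.5.5: "The number of unhealthy days and activity limitation days will be analyzed using analysis of variance techniques". For opioid dose, Section 11.5.7 says: "Morphine Equivalent Daily Dose (MEDD) will be treated as a continuous measure and analyzed using analysis of variance techniques". For the 5-level items, by contrast, Section 11.5.5 says "analysis of variance techniques on the ranks test will be used to test for differences by arm", so the absence of ranks for the other variables is fairly read as ANOVA on raw values.

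Neither sentence names a covariate, a time point, or whether the value or its change is analysed. Section 1.2 places the quality-of-life and opioid-sparing hypotheses at ten weeks. The calendar in Section 6 schedules the HRQOL-4 and opioid intake at baseline, midpoint and endpoint. Baseline adjustment is mentioned only for neuropathy improvement: the logistic model in Section 11.5.4 and, optionally, the repeated-measures model in Section 11.5.5.

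**The concern.** In a trial of 66 evaluable subjects, differences between people in health days and opioid dose are likely to be large and partly stable over ten weeks. An ANOVA by arm leaves all of that variation in the error term. It also leaves any chance baseline imbalance in the estimate, and with 22 controls such imbalance can be sizeable. The baseline value is the obvious covariate and is already on the case report form.

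A second issue is shape. The day counts are bounded. MEDD is zero for anyone not taking opioids; use is not an entry criterion, and Section 1.1.3 describes "opioids in severe cases unresponsive to other treatments", so many zeros are plausible. The plan gives no distribution check or supporting analysis for this.

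At stake is the precision and interpretability of two secondary endpoints and one exploratory endpoint.

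**Working it through.** **Inputs from the documents.** Evaluable subjects: 22 control and 44 acupuncture (Section 11.2). The only power figure is for the primary endpoint: Fisher's exact test, 0.10 against 0.35, two-sided alpha 0.20, at least 80%. Exact enumeration gives 81.7%, so it reproduces. For the day counts and MEDD the documents give no SD, share of zeros, effect size, baseline correlation or alpha. Everything below on those variables rests on assumptions.

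**Step 1: what baseline adjustment does in principle.** With correlation r between baseline and Week 10, ANCOVA multiplies the variance of the arm difference by about (1 − r²) × [1 + 1/(N − 4)]. The second factor is the price of estimating one slope (normal-theory approximation).

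- N = 66: 1 + 1/62 = 1.016.
- r = 0: variance × 1.016, so the standard error rises by about 0.8% (√1.016 = 1.008).
- Break-even: r² = 1 − 62/63 = 0.0159, so r = 0.13.
- r = 0.6 on the analysed scale: 0.64 × 1.016 = 0.65.

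**Step 2: size with bounded or zero-heavy data.** In simulation at 22/44 with a latent correlation of 0.6 and alpha 0.05, raw-scale power went from 49% to 58% in one day-count scenario and from 28% to 33% in one MEDD scenario. The overall range was about 3 to 9 points. Raw-scale power did not fall in any non-null scenario, type I error stayed near nominal, and gains were larger at 0.8.

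Consistency check with power ≈ Φ(δ − 1.96), ignoring the slope cost:

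- Days: δ = 1.960 − 0.025 = 1.935 before and 1.960 + 0.202 = 2.162 after. Variance ratio (1.935/2.162)² = 0.80; implied r = √0.20 = 0.45.
- MEDD: δ = 1.960 − 0.583 = 1.377 before and 1.960 − 0.440 = 1.520 after. Variance ratio (1.377/1.520)² = 0.82; implied r = √0.18 = 0.42.

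Bounds, zeros and long tails weaken a latent 0.6 to about 0.42–0.45 on the raw scale, so the gain is smaller than Step 1 gives for 0.6. It still corresponds to 66/0.82 ≈ 80 to 66/0.80 ≈ 83 unadjusted subjects.

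**Step 3: would ranks be better as the main analysis?** Power of raw and rank ANOVA, no baseline adjustment, 20,000 simulated trials per row. Unhealthy days: average of two correlated items, each with a mass at 0, a mass at 30 and a rounded exponential between; 40% item zeros in control. MEDD: 70% zeros in control, log-normal among users, log-SD 1.2.

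| Effect of treatment | Raw / rank, alpha 0.05 | Raw / rank, alpha 0.20 |
|---|---|---|
| Unhealthy days: item zeros 40% to 65% | 18.1% / 39.8% | 40.0% / 67.4% |
| Unhealthy days: non-zero amounts fall | 34.9% / 20.1% | 60.3% / 43.6% |
| Unhealthy days: both | 45.1% / 42.0% | 69.9% / 68.6% |
| MEDD: zeros 70% to 90% | 30.8% / 53.0% | 56.5% / 76.7% |
| MEDD: dose halved in users | 14.5% / 6.6% | 40.0% / 22.6% |
| MEDD: both | 51.7% / 57.6% | 77.7% / 79.3% |

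The single activity-limitation item, simulated with 40% zeros in control, behaves alike. Raising zeros to 65% gives 13.5% raw against 37.7% rank at 0.05. Lowering non-zero amounts gives 26.1% against 12.0%.

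Ranks win when treatment changes who is at zero. They lose when it lowers the amounts above zero, because ties at zero dilute the rank contrast. Raw ANOVA's type I error was 4.8–5.2% for days and 3.3–4.0% for MEDD at nominal 5%, and about 20% at nominal 20%.

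**The case against.** **A stronger reading.** A reader might infer that raw ANOVA throws away more than half the power of the rank method already used for the ordinal items, and that the plan should switch. The documents do not support this. They give no distributions, and a loss of that size appears only where treatment is assumed to raise the share of zeros, mostly at alpha 0.05, a level not stated for these endpoints. At 0.20, the only alpha in the plan, raw ANOVA kept 46–54% of the rank method's power for activity days, 51–66% for unhealthy days and 55–81% for MEDD in those favourable scenarios. Where only non-zero amounts fall, which fits an opioid-sparing aim at least as well, raw ANOVA had 1.3 to 3.1 times the rank method's power at 0.05. Unhealthy days average two items, so a value of 0 or 30 needs both items at the bound.

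**The case for leaving the plan alone.** ANOVA on numeric measures is conventional, its type I error holds here, and a mean difference in days or milligrams is easy to interpret. All of that stands, and it is why raw-scale analysis should remain the main one. It can also be said that analysis of variance techniques is broad enough to include ANCOVA. That is fair: the wording permits adjustment. It does not commit to it, however, and leaves the choice open until data from an unblinded trial are in hand.

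**A caution about the covariate.** Footnote 14 of the study calendar lets the HRQOL-4 be completed before or after randomization. A baseline answer given once the arm is known could be coloured by that knowledge. This limits how clean the covariate is for those subjects but does not remove its value.

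**Conclusion.** The point holds as an inexpensive improvement, not an error that threatens validity. The plan states no adjustment for a baseline value that it collects for all three variables. Adjusting helps once the raw-scale correlation passes about 0.13 and costs under 1% in standard error if there is none. The 3-to-9-point gain rests on assumed distributions, a latent correlation of 0.6 and alpha 0.05; none of these is in the documents.

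The possible excess of zeros and the bounds justify a supporting analysis. They do not justify replacing the main test, since the better method depends on how acupuncture acts, which is unknown. The consequences are confined to two secondary endpoints and one exploratory endpoint. The primary analysis is not touched.

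**What to change.** In Sections 11.5.5 and 11.5.7:

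1. State that unhealthy days, activity-limitation days and MEDD are each analysed at Week 10 by ANCOVA, with arm and that variable's own baseline value as terms, reporting the adjusted mean difference with a confidence interval.
2. Prespecify one sensitivity analysis: either rank ANCOVA with the ranked baseline value, or a two-part analysis (any against none, plus amount among non-zero subjects). If the two-part form is chosen, use a permutation p-value, because its asymptotic type I error ran at 5.6–6.3% for nominal 5% in simulation. Report medians and the proportion at zero by arm alongside.
3. State the significance level for these tests.
4. Say how a missing baseline value is handled, since the evaluable population requires only the neuropathy scores, and record whether the baseline questionnaire preceded randomization.

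The cost is SAP wording and a few lines of code. No new assessment or sample size change is needed.
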